4.6. Screening and Enrollment

Informed consent must be obtained before all the specific study procedures in this clinical trial. Subject is eligible for participation in this clinical trial after reviewing the inclusion and exclusion criteria. Candidates could be re-screened once if they did not fulfill the entry eligibility (failed screening) at the first screening visit. Subjects need to re-sign the ICF and obtain a new screening number during re-screening. Each eligible subject will be assigned a subject number to receive 3D185 treatment. The screening number and subject number will be assigned starting from the lowest number in chronological order.

5. STUDY POPULATION

5.1. Target Population

Subjects with advanced solid tumors who have no available standard therapy or who have failed standard therapies.

5.2. Inclusion Criteria

Subjects must meet all of the following criteria before they can be enrolled:

- 1. Age \geq 18 years.
- 2. Subjects must have a histological diagnosis of locally advanced or metastatic malignant solid tumors. Subjects must have failed the established standard treatment, or the standard treatment does not exist; or subjects are intolerant of or have refused to receive standard treatment. All subjects must have received at least one previous line of systemic treatment. Subjects with known genomic alterations for which there are approved therapies (e.g., ALK mutated NSCLC, microsatellite instability high/mismatch repair deficient solid tumors, EGFR NSCLC, etc.,) will have received such therapies prior to the enrolling in this study.
- 3. Subjects must have measurable or evaluable disease (according to RECIST 1.1, see Appendix 1);
- 4. ECOG Performance Status ≤ 2 .
- 5. Life expectancy ≥ 12 weeks.
- 6. Subjects must have normal levels of total serum calcium and total phosphate.
- 7. Subjects must have adequate organ and bone marrow function (subjects must not have received any hematopoietic growth factors, transfusion, or platelet within 1 week before the first dose).
 - CBC: neutrophils $\ge 1.5 \times 10^{9}$ /L, platelets $\ge 100 \times 10^{9}$ /L, hemoglobin ≥ 9.0 g/dL.
 - Liver function: total bilirubin $\leq 1.5 \times$ ULN, unless known to have Gilbert's disease; ALT/AST $\leq 2.5 \times$ ULN without liver metastasis; ALT/AST $\leq 5 \times$ ULN with liver metastasis;
 - Coagulation: $INR \le 1.5 \times ULN$ and $APTT \le 1.5 \times ULN$ (for subjects undergoing anticoagulant therapy, the Investigator should ensure that both INR and APTT are within the safe and effective treatment range).
 - Renal function: serum creatinine $\leq 1.5 \times \text{ULN}$, or creatinine clearance $\geq 60 \text{ mL/min}/1.73 \text{ m}^2$ in the condition of creatinine level > ULN; urine protein

analysis $\leq 1 + (\text{if } \geq 2+, 24 \text{ hours of urine protein test is required, if 24 hours urine protein <1 g, then allowed to enroll);$

- Adequate cardiac function: LVEF > 50% in two-dimensional echocardiography;
- 8. Subjects must have fully understood and voluntarily signed ICF for this study.

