9.2.1. Analysis Population

Full Analysis Set (FAS)

The FAS will include all subjects who received 3D185 treatment in this study. The FAS will be the primary population for evaluating all efficacy, safety and subject characteristics.

DLT Analysis Set (DLT set)

The DLT set will include all subjects who received at least \geq 75% of the planned doses of treatment and completed the safety assessment during DLT evaluation period. The frequency and severity of DLT will be analyzed.

PK Analysis Set (PKS)

The PK set will include subjects who have received at least one dose and have at least once evaluable PK sample collection after administration.

PD Analysis Set (PD set)

The PD set will include subjects who have received at least one dose and have at least once serum phosphate level measurement (serum biochemistry) after administration.

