9.3. Efficacy Analyses

The Investigator will perform the tumor assessment according to RECIST Version 1.1 at screening and every 8 weeks after the first dose in Cycle 1. The best overall response will be classified into progressive disease, SD, CR and PR. A summary by category and a listing will be provided.

ORR is defined as the proportion of subjects who achieve a BOR of CR or PR in the full analysis set. Estimate of ORR and its 95% exact confidence interval (CI) (Clopper-Pearson) will be provided.

The DCR is defined as the proportion of subjects whose BOR achieve a disease control (CR, PR, or SD) in the full analysis set. Estimate of DCR and its 95% exact CI (Clopper-Pearson) will also be provided.

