Appendix 1 The Response Evaluation Criteria In Solid Tumors (Recist) Guidelines

The text below was obtained from the following reference: Eisenhauer EA, Therese P, Bogaerts J, Schwartz LH, Sargent D, Ford R, et al. New response evaluation criteria in solid tumors: revised RECIST guideline (Version 1.1). Eur J Cancer 2009; 45:228-247.

DEFINITIONS

Response and progression will be evaluated in this trial using the international criteria proposed by the Response Evaluation Criteria in Solid Tumors (RECIST) Committee (Version 1.1). Changes in only the largest diameter (unidimensional measurement) of the tumor lesions are used in the RECIST criteria. Note: Lesions are either measurable or non-measurable using the criteria provided below. The term "evaluable" in reference to measurability will not be used because it does not provide additional meaning or accuracy.

Measurable Disease

Tumor lesions: Must be accurately measured in at least 1 dimension (longest diameter in the plane of measurement is to be recorded) with a minimum size of:

- 10 mm by CT scan (irrespective of scanner type) and MRI (no less than double the slice thickness and a minimum of 10 mm).
- 10 mm caliper measurement by clinical exam (when superficial).
- 20 mm by chest X-ray (if clearly defined and surrounded by aerated lung).

Malignant lymph nodes: To be considered pathologically enlarged and measurable, a lymph node must be ≥ 15 mm in short axis when assessed by CT scan (CT scan slice thickness recommended to be no greater than 5 mm). At baseline and in follow-up, only the short axis will be measured and followed.

Non-measurable Disease

All other lesions (or sites of disease), including small lesions (longest diameter ≥ 10 to < 15 mm with conventional techniques or < 10 mm using spiral CT scan), are considered non-measurable disease. Leptomeningeal disease, ascites, pleural, or pericardial effusion, inflammatory breast disease, lymphangitic involvement of skin or lung, abdominal

masses/abdominal organomegaly identified by physical examination that is not measurable by reproducible imaging techniques are all non-measurable.

Bone lesions:

- Bone scan, positron emission tomography (PET) scan, or plain films are not considered adequate imaging techniques to measure bone lesions. However, these techniques can be used to confirm the presence or disappearance of bone lesions

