Endoscopy, laparoscopy: The utilization of these techniques for objective tumor evaluation is not advised. However, they can be useful to confirm complete pathological response when biopsies are obtained or to determine relapse in trials where recurrence following CR or surgical resection is an endpoint.

Tumor markers: Tumor markers alone cannot be used to assess objective tumor response. If markers are initially above the upper normal limit, however, they must normalize for a subject to be considered in CR. Because tumor markers are disease specific, instructions for their measurement should be incorporated into protocols on a disease specific basis. Specific

guidelines for both CA-125 response (in recurrent ovarian cancer) and PSA response (in recurrent prostate cancer), have been published. In addition, the Gynecologic Cancer Intergroup has developed CA-125 progression criteria which are to be integrated with objective tumor assessment for use in first-line trials in ovarian cancer.

Cytology, histology: These techniques can be used to differentiate between PR and CR in rare cases if required by protocol (for example, residual lesions in tumor types such as germ cell tumors, where known residual benign tumors can remain). When effusions are known to be a potential adverse effect of treatment (e.g., with certain taxane compounds or angiogenesis inhibitors), the cytological confirmation of the neoplastic origin of any effusion that appears or worsens during treatment can be considered if the measurable tumor has met criteria for response or SD in order to differentiate between response (or SD) and PD.

RESPONSE CRITERIA

Evaluation of Target Lesions

Complete Response (CR): Disappearance of all target lesions. Any pathological lymph nodes (whether target or non-target) must have reduction in short axis to < 10 mm.

Partial Response (PR): At least a 30% decrease in the sum of diameters of target lesions, taking as reference the baseline sum diameters.

Progressive Disease (PD): At least a 20% increase in the sum of diameters of target lesions, taking as reference the smallest sum on study (this includes the baseline sum if that is the smallest on study). In addition to the relative increase of 20%, the sum must also demonstrate an absolute increase of at least 5 mm. (Note: the appearance of one or more new lesions is also considered progression).

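### Inclusion criterion 3 uses a term that Appendix 1 rejects, and the protocol does not say how subjects without target lesions enter ORR and DCR

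*Protocol*

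**What the plan says.** Section 5.2, criterion 3, with the same wording in the synopsis: "Subjects must have measurable or evaluable disease (according to RECIST 1.1, see Appendix 1". The definitions in Appendix 1 state that the term *evaluable* "in reference to measurability will not be used because it does not provide additional meaning or accuracy", and that lesions are either measurable or non-measurable.

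Appendix 1 defines PR as "At least a 30% decrease in the sum of diameters of target lesions, taking as reference the baseline sum diameters". It defines SD on the same sum of diameters. For non-target lesions it defines CR, Non-CR/Non-PD and PD, and one paragraph covers progression in patients who have only non-measurable disease. Table 8 (Best Overall Response) combines target, non-target and new-lesion findings into an overall response.

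Section 9.3 says: "The best overall response will be classified into progressive disease, SD, CR and PR". It then says "ORR is defined as the proportion of subjects who achieve a BOR of CR or PR in the full analysis set", and "The DCR is defined as the proportion of subjects whose BOR achieve a disease control (CR, PR, or SD) in the full analysis set". Section 9.2.1 says: "The FAS will include all subjects who received 3D185 treatment in this study". It sets no condition on measurable disease.

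On lesion size, Appendix 1 makes a tumour lesion measurable from 10 mm on CT, whatever the scanner. Under non-measurable disease it lists lesions with a longest diameter from 10 mm to below "15 mm with conventional techniques or < 10 mm using spiral CT scan".

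**The concern.** The criterion sends sites to Appendix 1 for the meaning of a word that Appendix 1 declines to use. The natural reading, though an inference, is that *evaluable* lets in subjects whose disease is all non-measurable, for example blastic bone lesions or an effusion. They have no target lesions, and the path from scan to ORR and DCR is incomplete for them. They cannot reach PR, and the commonest way of being under control has no category in section 9.3. Yet they count in both denominators.

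Two things are at stake. ORR is pulled down by the number of such subjects enrolled, and DCR depends on how each investigator labels the same tumour course. Initial i3+3 cohorts have 3 subjects, so one such subject can move a cohort's DCR by 1/3. Efficacy data also feed some decisions: the SMC considers them before adding an intermediate cohort (section 4.1), dose and efficacy are explored together (section 9.5), and tumour tissue is sought from subjects with CR, PR or SD (section 4.3.2), so unclassified subjects could be missed there.

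**Working it through.** The plan states no figure on this point, so there is none to reproduce. The check has three steps.

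**Step 1. Follow a subject without target lesions through Appendix 1 and section 9.3.**

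| Tumour course | Appendix 1 | Category in 9.3 | ORR | DCR |
|---|---|---|---|---|
| Progression or new lesion | PD, from the non-target definition, the non-measurable-only paragraph and the *Any* rows of Table 8 | PD | no | no |
| All lesions gone, markers normal | Meets non-target CR; Table 8 has no matching row | CR, arguably | yes, arguably | yes, arguably |
| Shrinkage short of disappearance | Cannot be PR; Non-CR/Non-PD | none | no | undefined |
| Persistence without progression | Non-CR/Non-PD | none | no | undefined |

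Every Table 8 row leading to CR, PR or SD needs a target-lesion result. The row for target lesions not all evaluated leads to NE, which section 9.3 does not list either.

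**Step 2. Size of the effect.** Let f be the share of treated subjects with only non-measurable disease. The protocol does not give it; I assume 10% to 30%. I also assume, for illustration, an ORR of 20% and a DCR of 60% in measurable subjects, and no CR among the others.

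- ORR in the FAS = (1 − f) × 20%. At f = 10%: 0.9 × 20% = 18%. At f = 30%: 0.7 × 20% = 14%.
- DCR in the FAS, Non-CR/Non-PD counted as failure = (1 − f) × 60%: 0.9 × 60% = 54%; 0.7 × 60% = 42%.
- DCR in the FAS, if all these subjects are stable and recorded as SD = (1 − f) × 60% + f: 54% + 10% = 64%; 42% + 30% = 72%.

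The same with whole subjects out of the stated maximum of 42, where k have no measurable lesion:

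| k | ORR, FAS | ORR, measurable | DCR, k as failures | DCR, k all as SD | DCR, measurable |
|---|---|---|---|---|---|
| 4 | 8/42 = 19.0% | 8/38 = 21.1% | 23/42 = 54.8% | 27/42 = 64.3% | 23/38 = 60.5% |
| 8 | 7/42 = 16.7% | 7/34 = 20.6% | 20/42 = 47.6% | 28/42 = 66.7% | 20/34 = 58.8% |
| 13 | 6/42 = 14.3% | 6/29 = 20.7% | 17/42 = 40.5% | 30/42 = 71.4% | 17/29 = 58.6% |

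At k = 8 the Clopper-Pearson 95% intervals for ORR are 7.0% to 31.4% (FAS) and 8.7% to 37.9% (measurable).

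**Step 3. Size limits.** Take a 12 mm non-nodal lesion. On spiral CT it is measurable under both statements. On non-spiral CT it is measurable by the 10 mm rule, which ignores scanner type, and non-measurable if *conventional techniques* includes non-spiral CT, as the contrast with spiral CT suggests. The target-lesion text of Appendix 1 uses the 10 to under 15 mm band only for the short axis of nodes.

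**The case against.** Several counter-arguments have force. A reader might infer that these subjects count against ORR and DCR whatever their tumour does. The documents do not support that: PD is explicitly provided for and is rightly a non-response, and complete disappearance with normal markers meets the non-target CR definition, so it can count in both rates. A reader might also infer that long-standing stable bone-only disease is scored as a DCR failure. No sentence says so. The mapping is missing, and an investigator who records SD makes it a success.

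The inputs are assumed, and no text supports a share as high as 30%. Keeping all treated subjects in the denominator is a stated and conservative choice. Detailed response derivation is often left to the SAP, which is not at hand.

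The SAP argument does not remove the point. Section 9.3 has already fixed the categories, numerators and denominators, and the clash over *evaluable* lies in the eligibility text and its appendix. The size-limit overlap is a separate, narrower matter and does not carry the ORR and DCR argument.

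**Conclusion.** The point holds in limited form. Criterion 3 relies on a term that its own appendix rejects. If it admits subjects without target lesions, they can never be PR, so FAS ORR is diluted by their share, CR aside: 20% reads as 18% to 14% for an assumed share of 10% to 30%. DCR is not shown to be biased in one direction; it is undefined. On the same assumptions a 60% DCR reads as 54% to 42% if Non-CR/Non-PD is a failure, and as 64% to 72% if all these subjects are stable and recorded as SD. The overlap in lesion size limits is real but confined to non-nodal lesions of 10 to under 15 mm on non-spiral CT.

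Severity is modest. ORR and DCR are secondary and descriptive. The MTD rests on DLT and safety data, the RPTD on PK, PD and safety, and the sample size on dose levels and DLTs.

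**What to change.** 1. In criterion 3 (section 5.2 and synopsis), replace *evaluable* with non-measurable disease as defined in Appendix 1. On the natural reading, eligibility does not change.
2. Add rows for subjects without target lesions to Table 8 (CR, Non-CR/Non-PD, PD, NE), and carry the same categories into section 9.3.
3. State in section 9.3 that Non-CR/Non-PD counts as disease control only if it meets the same minimum interval as SD. Appendix 1 puts that interval at generally no less than 6 weeks.
4. Report ORR in FAS subjects with measurable disease at baseline, beside the full FAS figure.
5. Reconcile the size limits in Appendix 1 so that no non-nodal lesion is both measurable and non-measurable on CT.

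The cost is wording and one extra denominator in the tables. The measurable-disease ORR has a slightly smaller n and a wider interval: in the k = 8 example the width is 37.9 − 8.7 = 29.2 percentage points, against 31.4 − 7.0 = 24.4 for the FAS.

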5.3. Exclusion Criteria

Subjects who meet any of the following criteria should be excluded from the study:

- 1. Subjects who received other investigational products or devices in other clinical trials within 4 weeks before the first dose.
- 2. Subjects who received anti-tumor therapy (except for mitomycin, nitrosourea, and fluorouracil oral drugs) within 4 weeks before the first dose, including but not limited to chemotherapy, radiotherapy (palliative radiotherapy is completed at least 2 weeks before the first dose can enroll), targeted therapy or immunotherapy.

Note: The last dose of mitomycin and nitrosourea should be at least 6 weeks before investigational product initiation; the last dose of oral fluorouracil such as tegafur and capecitabine should be at least 2 weeks before investigational product initiation.

- 3. Subjects who previously received selective FGFR1-3 inhibitor therapy.
- 4. Subjects who require the use of concomitant medications that prolong the QT/QTc interval.
- 5. Subjects who have previous toxicity of anti-tumor therapy that has not recovered to Grade 0 or 1. (alopecia, chemotherapy-induced peripheral neurotoxicity, and ototoxicity \leq Grade 2 can enroll).
- 6. Subjects who received CYP3A4 and/or CYP2C8 strong inhibitors or CYP3A4 strong inducers (see Appendix 6) within 14 days prior to the first dose and the subjects who need to continue using these drugs.
- Subjects who have any of the following eye diseases/conditions: 1) History of RPED;
 History of laser treatment or intraocular injection for macular degeneration; 3) History of dry or wet age-related macular degeneration; 4) History of RVO; 5) History of retinal degenerative diseases; 6) History of chorioretinal lesions.
- 8. Subjects who received clinical intervention for biliary obstruction 14 days prior to the first dose or the Investigator judges that the symptoms have not resolved or require anti-infective treatment.
- 9. Subjects who have gastrointestinal disorders that will affect oral administration or the Investigator judges that the absorption of 3D185 will be interfered.

- 10. Subjects underwent major surgery (except biopsy) within 4 weeks, or the surgical incision has not completely healed prior to the first dose.
- 11. Subjects who had clinically uncontrollable pleural effusion, ascites, or pericardial effusion within 2 weeks prior to the first dose.
- 12. Subjects who have symptomatic brain metastases or spinal cord compression. For the subjects, who have previously treated for brain metastases, if the clinical condition is stable and imaging evidence does not show disease progression within 4 weeks prior to the first dose, and do not need corticosteroid treatment within 2 weeks prior to the first dose, can enroll.
- 13. Subjects who have active bacterial or fungal infections (CTCAE Grade ≥ 2) that required systemic treatment within 14 days prior to the first dose.
- 14. Subjects who have active HBV infection (HBV DNA \geq 1000 copies/mL) and/or HCV antibody testing positive;
- 15. Subjects who have clinically significant cardiovascular diseases that occurred 6 months prior to first dose. Cardiovascular diseases include, but not limited to follows: acute myocardial infarction; severe/unstable angina; cerebrovascular accident or transient ischemic attack; congestive heart failure (NYHA > Class II, see Appendix 3); arrhythmias that require antiarrhythmic treatment except for beta blockers or digoxin; repeated ECG with QTc interval > 450 ms; high blood pressure that cannot be controlled by antihypertensive drugs (systolic blood pressure > 150 mm Hg, diastolic blood pressure > 100 mmHg).
- 16. Subjects who have clinically significant abnormal serum electrolyte levels.
- 17. Subjects who are receiving warfarin (low-dose warfarin up to 2 mg/day is allowed); or receiving antiplatelet anticoagulant therapy (aspirin at dose ≥ 300 mg/day, clopidogrel at dose ≥75 mg/day).
- 18. Female subjects in pregnancy or lactation. Male subjects or female subjects at reproductive ages who are unwilling to receive effective contraceptive measures.
- 19. Subjects who are judged by the Investigator to be unsuitable for this study.

5.4. Subject Study Completion and Withdrawal Criteria

5.4.1. Subject Study Completion

A subject will be considered to complete study if he/she has a valid PK profile and has not withdrawn from the study prior to the DLT evaluation period (first treatment cycle). A subject also will be considered to complete study if he/she discontinued study treatment due to a DLT with or without a valid PK profile.

5.4.2. Subject Withdrawal/Discontinuation

If a subject has any medical condition and the Investigator believes that his or her continued participation in the study may jeopardize the safety, the Investigator has the right to decide that the subject will discontinue the study treatment early. All subjects, who signed the ICF and screened eligible into the trial, have the right at any time to withdraw or discontinue from the treatment of investigational product. In addition, a subject may be withdrawn by the Investigator if he/she violates the study plan or management and/or other safety reasons.

When a subject discontinues/withdraws prior to study completion, all applicable activities scheduled for the safety follow-up visit should be performed. Any drug-related AEs which are present at the time of discontinuation/withdrawal should be followed in accordance with the safety requirements.

During the treatment period, subjects can receive 3D185 treatment until one of the following events occurs:

- Subject withdrew consent;
- Progressive disease;
- Death;
- Unacceptable treatment toxicity;
- Start other anti-cancer therapy;
- The Investigator determines it is in the best benefit of the subject to discontinue the investigational product treatment;
- Poor compliance or severe protocol violations, and have an impact on drug tolerance, safety, or PK evaluation;
- Pregnancy during the treatment period;
- Lost to follow-up;
- Others.

Subjects who stop treatment prior to the documentation of disease progression will undergo repeated imaging for tumor response assessments at the frequency according to protocol until unequivocal disease progression is documented or the subject starts new anticancer therapies or subject withdraws consent from the trial, whichever occurs first. Subjects who withdraw from the study for clinical or symptomatic deterioration before objective documentation of disease progression. Every effort will be made to confirm a clinical diagnosis of disease progression by imaging.

